#### Interventions

The participants are randomly assigned to one of three conditions consisting of: 1) a Weight Gain Prevention intervention; 2) a Blood Pressure Control Program focusing on lifestyle modification; or 3) a Usual Lifestyle condition. In addition to the lifestyle interventions being evaluated in the present study, participants will be instructed to continue to have their blood pressure managed by their primary care provider.

##### 1. Weight Gain Prevention Intervention

There have been several successful behavioral trials that targeted weight control and/or nutritional modification for the control of Blood Pressure including the multi-center clinical trial TONE; Trials of Nonpharmacologic Interventions in the Elderly. The Weight Gain Prevention intervention used in this study was derived from the Weight Loss Only program developed for TONE. The focus of the intervention will be on preventing weight gain following smoking cessation. Because participants will enter the study at a wide range of body weights, the emphasis will be on preventing the weight gain that accompanies quitting smoking rather than weight loss per se. Each participant will be provided with a copy of The CalorieKing Calorie, Fat & Carbohydrate Counter 2007 Edition, published by Dietclub.

Participants will be advised to engage in 30 minutes or more of moderate intensity activity on most, and preferably all, days of the week. Moderate intensity activities include those that range from 3.0 to 6.0 METS, or 4 to 7 kcal x minute-1. Examples include brisk walking, cycling at moderate speed, and general household cleaning. Participants will be given flexibility in both the specific types of moderate activity they choose to engage in, as well as the method in which they choose to accumulate their activity over the course of the day (e.g., several short bouts of activity vs. a single 30-minute period of exercise).

The Weight Gain Prevention intervention will consist of five individual and 12 group sessions lasting 30-60 minutes conducted over a 12-week period. Sessions will be held in person, but can be made up over the phone if the participant is unable to attend a session. As noted above, the intervention is modeled after the TONE Weight Loss Only protocol. The group sessions, which are largely didactic in format but also include group discussion, address a variety of proven weight management strategies including nutrition education, behavioral skills training, problem solving, "relapse" prevention, and moderate increases in physical activity. Participants also will be instructed to self-monitor their dietary intake and physical activity as a means of gaining additional insight into their behavior patterns, as well as to evaluate success in meeting behavioral goals.

Each of the individual sessions will focus on reviewing participants' success with meeting dietary, physical activity, and weight goals, and problem solving strategies for increasing adherence and success. Consequently, these sessions will provide more specific, individualized instruction tailored to the needs of each individual participant.

At each session a small snack will be provided to the participants, prepared by the bionutrition department of the General Clinical Research Center (GCRC). The snacks will be designed to be low calorie, nutrient dense, and will illustrate the principles of what is being discussed at the intervention.

At all sessions, tobacco use status, serious adverse event information, and weight will be recorded. At the individual sessions, the participant will be asked about concomitant medications (smoking cessation, weight management, and blood pressure medications only), followed by an expired air carbon monoxide (CO) assessment, and a blood pressure reading. The weight gain prevention intervention portion of the study including 12 group sessions and 5 individual sessions will take approximately 17 hours to complete.

## 2. Blood Pressure Control Intervention

The intervention for those assigned to the Blood Pressure Control condition is patterned after the TONE Weight Loss + Sodium Restriction program. The rationale for addressing weight gain prevention in the Blood Pressure Control intervention is based on the well-documented relationships between smoking, dietary intake, body weight, and blood pressure. Smoking cessation typically leads to weight gain ([name] et al., 2001; Ward, Klesges, & [name], 2001). Increases in body weight, consequently, are associated with an elevation in BP (Huang et al., 1998; Juhaeri et al., 2002). Thus, the goal of the intervention is to limit cessation-induced weight gain in order to improve BP control. Each participant will be provided with a copy of The CalorieKing Calorie, Fat & Carbohydrate Counter 2007 Edition, published by Dietclub.

Results from past studies indicate that the weight gain that occurs following smoking cessation is due primarily to increases in energy intake, although the removal of the acute thermic effect of nicotine also may play a role (Stamford et al., 1986; [name] et al., 2000; 2001). Therefore, the intervention is aimed at reducing the positive energy balance that occurs following smoking cessation by limiting postcessation increases in energy intake, and promoting increased energy expenditure through physical activity.

In addition to promoting weight control, the Blood Pressure Control intervention will target a variety of nutritional recommendations designed to lower blood pressure, including sodium restriction. Numerous epidemiological studies have demonstrated an inverse association between dietary sodium and BP (Elliott et al., 1996; Stamler, 1997). Further, clinical trials have shown sodium restriction to be associated with a reduction in BP, particularly among those with hypertension (He & MacGregor, 2002; Sacks et al. 2001). In accordance with the TONE combined Weight Loss + Sodium Restriction intervention, the goal for sodium intake will be  $\leq 1500$  mg/day. Although this level is significantly less than that typically consumed in the American diet, it is considerably higher than what is required to meet the body's nutritional needs (Mahan & Escott-Stump, 1996). This level of sodium restriction was associated with a significant decrease in BP in TONE, both when used as a solitary intervention and when combined with weight loss (Appel et al., 2001; Whelton et al., 1998).

In addition to sodium restriction, the BP Control intervention will incorporate the

nutritional recommendations that are included in the DASH (Dietary Approaches to Stopping Hypertension) diet plan (Vogt et al., 1999). DASH was a multicenter randomized feeding study that compared the impact of three diet plans on blood pressure. The combination diet that was developed for DASH is rich in fruits, vegetables, and low-fat dairy products, and includes whole grains, poultry, fish, and nuts. It also emphasizes reduced consumption of red meat, sweets, and sweetened beverages. Nutritionally, the plan produces a diet that is considerably higher in potassium, magnesium, calcium, fiber, and protein than is typically consumed in the U.S. and lower in dietary fat and cholesterol (Vogt et al., 1999). The combination diet was associated with the most favorable blood pressure outcomes in the original DASH trial (Appel et al., 1997), and has been recommended by the National High Blood Pressure Education Program for preventing and managing hypertension (Windhauser et al., 1999).

Although the DASH dietary plan involves a wide range of dietary goals targeting several food and nutrient groups, it was specifically designed to be practical, palatable, and feasible for implementation in the general population (Vogt et al., 1999). Findings from the original DASH study suggested that adherence to the diet plan was exceptionally high (> 90%) based on both subjective and objective measures (Windhauser et al., 1999). Thus, we are confident that the DASH combination diet can be successfully adopted by participants in this trial.

As with the Weight Gain Prevention the primary rationale for incorporating increases in physical activity is for the weight controlling effects (Blair, 1993; Grilo et al., 1993). However, studies also have demonstrated hypotensive benefits from physical activity that are independent of weight loss (Arroll & Beaglehole, 1992; Whelton et al., 2002). Thus, physical activity appears to provide multiple benefits in terms of BP control, and will comprise an important component of the intervention. Because several studies have shown strength training to be effective at reducing BP (see Kelly & Kelly, 2000 for review), participants also will be encouraged to engage in resistance training as well as aerobic activities. Participants will be given flexibility both in the specific types of moderate activity they choose to engage in, as well as the method in which they choose to accumulate their activity over the course of the day (e.g., several short bouts of activity vs. a single 30-minute period of exercise).

The BP Control Intervention will consist of five individual and 12 group sessions lasting 30-60 minutes conducted over a 12-week period. Sessions will be held in person, but can be made up over the phone if the participant is unable to attend a session. As noted above, the intervention will be modeled after the TONE Weight Loss + Sodium Restriction protocol. Individual sessions will focus on reviewing participants' success with meeting treatment goals and problem solving strategies for increasing adherence and success. Consequently, these sessions will provide specific, individualized instruction tailored to the needs of each participant. The group sessions will address a variety of proven educational and behavioral strategies for modifying diet and physical activity. Several of the intervention components involve strategies similar to those included in the smoking cessation intervention (e.g., self-monitoring, problem solving, relapse prevention). Attempts will be made to emphasize these similarities and to build on previous mastery experiences as a means of promoting continuity across intervention components and enhancing self-efficacy.

At each session a small snack will be provided to the participants, prepared by the bionutrition department of the General Clinical Research Center (GCRC). The snacks will be designed to be low calorie, nutrient dense, and will illustrate the principles of what is

being discussed at the intervention.

At all sessions, tobacco use status, serious adverse event information, and weight will be recorded. At the individual sessions, the participant will be asked about concomitant medication (smoking cessation, weight management, and blood pressure medications only), followed by an expired air carbon monoxide (CO) assessment, and a blood pressure reading. The Blood Pressure Control intervention portion of the study including 12 group sessions and 5 individual sessions will take approximately 17 hours to complete.

Although the two proposed lifestyle interventions may seem fairly intensive (four session smoking cessation intervention plus a four-month BP Control or Weight Gain Prevention program), brief interventions are not likely to be successful at modifying multiple complex behaviors such as smoking, diet, and physical activity. Additionally, participants are likely to be highly motivated to make these lifestyle changes given their high-risk status (Kastarinen et al., 2002; Nothwehr & Perkins, 2002). Furthermore, the length of the intervention is comparable to that used by Spring et al. (2004), one of the few studies to date to demonstrate a significant reduction in postcessation weight gain following lifestyle modification. In addition, the BP Control and Weight Gain Prevention interventions, which are by far the most intensive components of the intervention, were previously shown to be acceptable and successful at reducing weight and BP among patients with hypertension (Whelton et al., 1998). Attendance at the intervention sessions during the first nine months, the most intensive phase of the intervention, averaged 88% (Chao et al., 2000). Attendance at follow-up data collection visits conducted out to 30 months averaged over 85% (Whelton et al., 1998). To date, attendance at the group and individual sessions in the present study at another site has averaged 91% (when make up sessions are taken into consideration). To reinforce attendance, small, low-cost items will be given out at some of the intervention group sessions (for both the Blood Pressure Control group and the Weight Gain Prevention group). The items, for example, may advertise the study logo, or may reinforce healthy behaviors.

### 3. Usual Lifestyle Condition

To determine the relative effectiveness of the Blood Pressure Control and Weight Gain Prevention interventions, results will be compared to participants assigned to a Usual Lifestyle condition. Participants in this group will receive self-help materials designed to help them manage their body weight and blood pressure. These will consist of two books published by Mayo Clinic Health Information: Mayo Clinic Healthy Weight for Everybody and Mayo Clinic on High Blood Pressure: Taking Control of Your Hypertension. However, they will not receive any additional instructions for making lifestyle changes other than they would normally receive from their primary care provider.

### Follow-up Visits

Two follow-up visits will be conducted at six- and 12-months post cessation. Participants will be asked to return to the Preventive Intervention Center for these visits. The procedures performed at these visits will be largely the same. The participant will be asked to report their current smoking status, followed by an expired air carbon monoxide (CO) assessment. For those who fail the CO test (i.e., CO > 10 ppm), yet still claim to be a nonsmoker, a salivary cotinine test will be given to provide a confirming/disconfirming assessment. For those who fail the CO test but report using a nicotine replacement therapy (which would alter the results of the salivary cotinine

test) will instead be tested for thiocyanate via blood draw.

Vitals will also be taken (weight, pulse, blood pressure and waist circumference). Percentage of body fat will be measured using a bioelectrical impedance analysis. Serious adverse event information, and concomitant medication (smoking cessation, weight management, and blood pressure medications only) will be recorded. Current physical activity level will be assessed using the long version of the International Physical Activity Questionnaire (IPAQ). The participant will also be asked to report on their dietary intake by completing two commonly-used dietary screeners. Percent of energy intake from fat will be assessed using the National Cancer Institute (NCI) Fat Screener. Fruit and vegetable intake will be assessed using the All Day version of the NCI Fruit and Vegetable Screener.

The participant will be asked to complete some questionnaires to assess self-efficacy and outcome expectations related to smoking cessation, weight control, and physical activity. Self-efficacy for smoking cessation will be assessed using the Smoking Self-Efficacy Questionnaire. Self-efficacy for physical activity will be measured with the Self Efficacy for Exercise Behaviors Survey, and self-efficacy for weight control will be assessed with the Weight Efficacy Lifestyle Questionnaire. Outcome expectations regarding smoking cessation, physical activity, and weight control will be assessed using measures of decisional balance. In addition, worries about weight gain after quitting smoking will be assessed with a Weight Concerns Scale. Participants will also be asked to complete a 25-item health and lifestyle questionnaire that assesses the following domains: self-perceived health, health related quality of life, changes in blood pressure and blood pressure medication, smoking status and quit attempts, physical activity, body weight and weight control behaviors, dietary intake, and lifestyle changes made in an effort to control blood pressure. Participants who did not quit smoking and who were not randomized to treatment conditions will also be asked to complete this questionnaire by phone.

Lastly, participants will be instructed to test five overnight urine samples at home using chloride titrator sticks in order to measure baseline dietary sodium intake. Participants will be instructed to collect overnight urine samples (2200 to 0600) each morning in containers provided by the study laboratory. Participants will then place a chloride titrator stick into the urine sample for a period of 20 minutes. After the column becomes saturated, a moisture sensitive signal appears at the top. A line appears on the column providing a value ranging from 0.0 to 10.0. The participant will mark the titrator stick reading on a chart provided by the study staff. After five overnight samples the participant will mail the chart back to the study staff.

Participants assigned to either the Weight Gain Prevention or Blood Pressure Control intervention will be asked to complete a brief (9-item) questionnaire at the six-month follow-up to assess their impressions of the helpfulness and effectiveness of various parts of the lifestyle intervention.

The six and 12 month follow-up visits will take approximately 2 hours to complete each, plus the participant's at-home time collecting overnight urine samples. For participants who attend the 12 month visit, we will provide them with a certificate of appreciation to thank them for their participation in the study. If they are still smoke free, we will also give them the certificate of achievement to recognize their hard work.

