#### Smoking Cessation

All participants who meet screening criteria at the baseline visit will come back and meet for a total of four sessions with a health educator to address smoking cessation. The study team will try to schedule the sessions as described here, but flexibility will be allowed for life circumstances, holidays, weather, etc. Sessions may be conducted over the phone or in person. In Session 1, about 1 week after the baseline visit but before the participant's "quit" date, the focus will be on preparing to quit and surviving the first days as a nonsmoker. Establishing quitting rituals, building support, and using the "Five A's" (Anticipate, Avoid, Alter, Alternatives, and Active) will be emphasized. Session 2, scheduled within 24 hours of the quit attempt, addresses maintaining motivation and coping with negative emotions and nicotine withdrawal. Session 3 will occur approximately one week postcessation. As in all sessions, problem solving and support building will be emphasized. In addition, dealing with negative cognitions will be addressed. In the final session, conducted three weeks postcessation, preventing relapse will be the emphasis. In a mailing prior to this session, participants are asked to do homework before the session that will facilitate making an individualized relapse prevention plan. Participants are asked to identify high-risk situations and difficulties encountered in previous cessation attempts and are walked through a series of suggestions in the event of a slip.

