At each session the participant will be asked to report their current smoking status, followed by an expired air carbon monoxide (CO) assessment. On the forth cessation visit if the participant fails the CO test (i.e., CO > 10 ppm), yet still claims to be abstinent from smoking, a salivary cotinine test will be given to provide a confirming/disconfirming assessment. Cotinine is a specific major metabolite of nicotine that can be detected in saliva for 45 to 80 hours. The procedure involves having the subject place a small cotton dental roll on his/her tongue for three minutes. At the end of this time, the subject expels the roll into a small vial. For those participants who fail the CO test but report using a nicotine replacement therapy (which would alter the results of the salivary cotinine test) will instead be tested for thiocyanate via blood draw. The amount of thiocyanate in a person's blood provides information about their level of exposure to cigarette smoke. Adverse events and concomitant medications will be reviewed at each session. Each of the 4 sessions will take approximately 1 hour to complete. If the session is completed over the phone, the physical assessments will not

be taken.

Next, there will be 4 follow-up phone calls. These calls are used to identify early relapse, encourage participants, and provide support. They also are used to review materials and information provided during the sessions with the health educator. The calls are made in the first few months of the intervention. Calls will take approximately 10-15 minutes each to complete.

Finally, participants receive six mailings over the course of the study. The first mailing, sent one week postcessation, provides information and a worksheet to facilitate relapse prevention. The next mailing, sent four weeks postcessation, focuses on coming off the patch. Nine weeks into the study, participants receive a mailing about stress management. The remaining three mailings are sent during months 7, 9, and 11. The topics covered include secondhand smoke, helping friends/family members to quit smoking, and a general review of some of cessation program items.

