#### Randomization

Following the smoking cessation sessions, all participants who are abstinent from smoking based on two-week prolonged abstinence criteria will come in for a randomization visit (Please note that in order to improve clarity, this visit is referred to as the Group Assignment Visit in the Participant Consent Form). The participant will be asked to report their current smoking status, followed by an expired air carbon monoxide (CO) assessment. For those who fail the CO test (i.e., CO > 10 ppm), yet still claim to be abstinent from smoking, a salivary cotinine test will be given to provide a confirming/disconfirming assessment. For those who fail the CO test but report using a nicotine replacement therapy (which would alter the results of the salivary cotinine test) will instead be tested for thiocyanate via blood draw. Participants who do not successfully quit smoking will be given a chance to recycle through the smoking cessation intervention a second time.

At this visit the study staff will perform an interval medical history with the participant, to ensure nothing critical has changed from the screening visit. Vitals will also be taken again (weight, pulse and blood pressure). Waist circumference will also be measured. Percentage of body fat will be measured using a bioelectrical impedance analysis. Inclusion/exclusion criteria will be reviewed again. Adverse events and concomitant medications will be reviewed. The participant will have an electrocardiogram (ECG) performed by study staff and reviewed by a physician for evidence of 2nd or 3rd degree AV block and to assess for previous silent myocardial infarction. If the ECG results are inconclusive, the participant will be advised to consult his/her primary care provider and will not be able to participate in the study. If the participant is still interested in participating in the study, he/she should contact his/her primary care provider in order to perform an exercise stress test. The test would be conducted under the supervision of the primary care provider. If the results of the exercise stress test indicate that it is safe for the individual to enroll in the study, and the primary care provider and the

study physician clear them for participation, then they will be allowed to enroll provided they meet other eligibility criteria.

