## IV. Nicotine Replacement Use

Although most persons do not experience any major adverse effects from the nicotine patch or nicotine gum, it is possible that a participant could experience any of the following side effects. All participants will be questioned or evaluated for side effects at each follow-up visit:

- a. Skin erythema, pruritus, edema, burning, and rash at the application site of the patch
- b. Headache, Dizziness, dry mouth
- c. Arthralgia, myalgia, back pain
- d. Abdominal pain, constipation, diarrhea, dyspepsia, flatulence, nausea, vomiting, heartburn, hiccups
- e. Impaired concentration, depression, headache, insomnia, abnormal dreams, nervousness
- f. Cough, sinusitis
- g. Allergy to nicotine
- h. Cardiovascular side effects (cardiac arrhythmia, tachycardia, vasospasm, elevated blood pressure)
- i. Jaw or mouth soreness from chewing the gum

Although these adverse events have been reported in those who use nicotine replacement therapy, they have been infrequent and are less likely to be observed in persons who are regular cigarette smokers. In addition, many of these same symptoms are reported by persons who quit smoking without nicotine replacement therapy and have been attributed to nicotine withdrawal from smoking cessation.

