## V. Physical Activity

Increasing one's physical activity slightly increases the risk of a cardiac event such as angina or a myocardial infarction. Steps will be taken, as described above, to minimize this risk among participants in the study.

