placed on the 14 mg patch, participants who report smoking 5 - 9 cigarettes will be initially placed on the 7 mg patch. If a participant is initially placed on the 21 mg patch we will use the following dosing schedule: 21 mg patch for two weeks, 14 mg patch for two weeks, 7 mg patch for two weeks, and then off. If a participant is initially placed on the 14 mg patch, we will use the following dosing schedule: 14 mg patch for two weeks, 7 mg patch for four weeks, and then off. If a participant is initially placed on the 7 mg patch, we will use the following dosing schedule: 7 mg patch for six weeks, and then off. Participants will start the nicotine patch on their quit date. This should coincide with Session 2 of the behavioral smoking cessation intervention. The patch will be discontinued after six weeks of use. Nicotine gum is an over-the-counter product that will be given in 2mg pieces, with up to 3 boxes (approximately 6 weeks of regular use).

Participants will have the side effects of nicotine replacement discussed with them and receive detailed instructions regarding proper use of the patch and of the gum. We will monitor concomitant smoking and nicotine replacement use. As a safety measure, nicotine replacement use will be discontinued in a participant that clearly demonstrates repeated concomitant smoking and nicotine replacement therapy use. We also will monitor all participants for use of other pharmacological agents for smoking cessation (e.g., bupropion, varenicline, nicotine nasal spray, nicotine inhaler, nicotine lozenge).

Potential side effects of medication (NRT) will be monitored at each clinic visit while participants are using the patch. Additionally, participants will be given a pager/voice mail number that they can call in the event of adverse effects. Our experience with nicotine replacement is that there will be very few calls to report "adverse" effects. Most calls that we do get occur predictably within the first three days of cessation and are actually symptoms of smoking withdrawal that are being confused as side effects (e.g., craving for a cigarette). Most of the remaining adverse effects are the result of improper use of the product (e.g., failure to move the patch from one area to another). Remediation will be given as necessary. In the case of a true adverse effect, an RN or study physician will be on call to discuss the problem with the participant and, if necessary, to take him or her off of the product.

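### After randomization the visit procedures list only serious adverse events, against the protocol's own risk sections, so non-serious events rest mainly on volunteered reports and on unequal contact between arms

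*Protocol*

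**What the plan says.** Protocol VII.E.6 collects all adverse events in the first part of the study. They are recorded at the baseline visit. For the cessation sessions the text is "Adverse events and concomitant medications will be reviewed at each session", and for the randomization visit "Adverse events and concomitant medications will be reviewed".

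The rule then narrows. For the Weight Gain Prevention program the protocol says "At all sessions, tobacco use status, serious adverse event information, and weight will be recorded", and the Blood Pressure Control section repeats that sentence. For the 6- and 12-month visits it says "Serious adverse event information, and concomitant medication (smoking cessation, weight management, and blood pressure medications only) will be recorded". The Usual Lifestyle section describes no visit of its own. The two symptom questionnaires (PAR-Q and Rose Angina) are given at baseline and at randomization and do not appear among the follow-up procedures.

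The risk sections read differently. VIII.1, on nicotine replacement, says "All participants will be questioned or evaluated for side effects at each follow-up visit". VIII.2, on the same subject, has side effects watched at each clinic visit for as long as the patch is in use. VIII.2, on monitoring, has any adverse experience that is reported written up in full. On exercise, VIII.1 says "Increasing one's physical activity slightly increases the risk of a cardiac event such as angina or a myocardial infarction".

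The SAP contains no adverse event analysis.

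**The concern.** The narrower rule takes effect just as several exposures begin or are still running. Study gum is first supplied at the randomization visit, the prescribed activity belongs to the randomized programs, and the patch course may not be finished. The activity risk that the protocol names includes angina, which need not meet a seriousness criterion. Most of the nicotine replacement effects listed in VIII.1 are likewise of a kind that is usually non-serious.

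An external committee is asked to weigh risk against benefit (VIII.2 and VIII.4). If non-serious events were not systematically asked about after randomization, a low count from that period says little about safety. Events found through sessions would also come disproportionately from the two active arms, because only those arms have sessions.

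**Working it through.** No planned figure is at issue, so the check sets the passages side by side and then does timeline and contact arithmetic.

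**1. What is listed at each contact**

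| Contact | Procedures (VII.E.6) | Risk sections (VIII.1, VIII.2) |
|---|---|---|
| Baseline, cessation sessions, randomization | all adverse events | consistent |
| Active-arm sessions | serious events only | nicotine replacement effects at each clinic visit during patch use |
| 6- and 12-month visits | serious events only | patch and gum side effects at each follow-up visit |
| Any time | take-home log for any event | any reported event is recorded |

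The second and third rows conflict. The fourth depends on the participant coming forward.

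**2. Exposure after the change of rule**

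- Patch: use starts on the quit date, and each of the three schedules totals six weeks (2 + 2 + 2; 2 + 4; 6). On the last cessation session the protocol says "In the final session, conducted three weeks postcessation, preventing relapse will be the emphasis", and XI.2 places eligibility for randomization at the end of a 4-week cessation phase. I therefore assume randomization at week r = 3 to 4 after quitting. Patch weeks remaining = 6 − r, which gives 3 weeks at r = 3, 2 weeks at r = 4, and none at r = 6 or later. Participants who quit on their own skip the cessation phase and its patch.
- Gum: one box of about 110 pieces at randomization and up to two more on request, so at most 3 × 110 = 330 pieces, all supplied from the change onward.
- Prescribed activity: all 12 weeks of both active programs follow randomization.

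**3. Contacts after randomization that list event collection**

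- Each active arm: 12 group sessions + 5 individual sessions + 2 follow-up visits = 19.
- Usual Lifestyle: 2 follow-up visits.
- With six months after quitting taken as 26 weeks, the first Usual Lifestyle contact comes 26 − 4 = 22 to 26 − 3 = 23 weeks after randomization, for those randomized at week 3 to 4.

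The four cessation support calls are not counted, because their described purpose is relapse detection, encouragement and review of materials, with no mention of adverse events.

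**4. Exertional symptoms**

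The VIII.1 questioning concerns patch and gum, and the VIII.2 clinic-visit monitoring concerns nicotine replacement. Neither covers exercise. No symptom questionnaire is listed after randomization, and the domains named for the 6- and 12-month health and lifestyle questionnaire do not include exertional symptoms. That leaves self-report.

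**The case against.** A reader might infer that after randomization staff ask about serious events only and that everything else goes unrecorded. The documents do not support that. VIII.1 and VIII.2 promise questioning about nicotine replacement effects at later visits. VIII.2 has any reported adverse experience recorded, without limit to serious events or to the period before randomization. Participants are told to keep a record and notify the center, and they carry logs for reporting events at the next visit. Blood pressure is measured at the individual sessions and follow-up visits, so an elevated reading, one of the listed nicotine effects, would be seen. An operations manual said to cover adverse events and side effects is not among the documents and may settle the matter. This stands, and it limits the point to a contradiction and to weak solicitation.

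These provisions do not close the gap. What the protocol calls follow-up visits fall at six and 12 months, after the six-week patch course and, at regular use, after about six weeks of gum. The clinic-visit monitoring applies only during patch use, conflicts with the session lists in the active arms, and has no visit to attach to in Usual Lifestyle before six months. The record, notification and log provisions are passive. A log entry made in Usual Lifestyle waits for a visit whose list names serious events only.

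A reader might also want to turn the attrition plan into a number of affected non-quitters, or to state a percentage of nicotine replacement time left uncovered. The documents do not support such figures. Non-quitters may repeat the cessation program with its full review, nicotine replacement is stopped for repeated concurrent smoking, gum is optional, and the gum instructions say not to combine it with other nicotine replacement, so its timing against the patch is unknown.

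Finally, the SAP plans no between-arm adverse event comparison, so unequal contact biases no planned analysis. That is correct. The risk lies in how safety counts are read by the monitoring committee and in the manuscripts.

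**Conclusion.** The contradiction is real and rests on exact text: three procedure passages list serious events only after randomization, against two risk passages that promise side-effect questioning. If the visits followed the procedures section, non-serious events after randomization were mainly volunteered. The gap is clearest for exertional symptoms, a named risk of the intervention for which no prompt is described once the activity begins.

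Its reach is all study-supplied gum, all 12 weeks of the activity programs and about 2 to 3 patch weeks. The patch figure depends on randomization at week 3 to 4 and falls to zero at week 6 or later. Listed contacts are 19 against 2. The documents do not show what was actually asked, so loss of events is possible but not established. The efficacy analyses are untouched.

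**What to change.** Reconcile the session and follow-up visit lists in VII.E.6 with VIII.1 and VIII.2 by recording adverse events, including exertional symptoms, in place of serious events alone at the contacts already planned. In a running trial this would cost a few minutes per contact and more forms.

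Protocol I.4 and VII.A.4 state that collection is complete and that only analysis and manuscripts remain, so the usable fix is in reporting:

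- Check the operations manual and the case report forms for what was asked at sessions and at the 6- and 12-month visits.
- If they show serious events only, state in the safety report that non-serious events were systematically solicited only up to randomization, and do not present later non-serious counts as complete.
- Compare arms only on serious events from the common 6- and 12-month visits, after confirming that those forms covered the whole interval since the previous common visit. Describe session-reported events by arm without comparison.
- If the forms show that all events were asked about, say so and correct the description of the procedures.

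The cost is a document check and a few sentences of text. The price is that the report can say less about non-serious safety after randomization.
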